#### (v) Research volunteer databases

Relevant research volunteer database searches, including SHARE, will be employed to identify patients receiving oral iron treatment to identify potential participants. The research team will provide study information including a brief Participant Information Brochure, reply slip and pre-paid reply envelope.

#### 5.1.4 Invitation Mailings

All invitation packs will be sent via HIC. HIC is a University of Dundee research support unit within the Tayside Medical Science Centre (TASC). All services provided by HIC are delivered within an ISO 270001 certified secure environment to ensure data is managed safely and in compliance with Data Protection legislation. The identified invitation lists will be stored securely within the NHS network. The invitation pack will consist of an invitation letter with a

reply slip, brief information sheet/leaflet and pre-paid return envelope. The research team will not have access to this confidential invitation list. HIC will also send any reminders with the relevant PIS.

Participants can indicate their interest in the study by completing and returning the reply slip using the pre-paid envelope or by calling/e-mailing the study team. Those interested will be sent information sheet. HIC will upload all positive replies allowing the relevant study team access contact details of the potential participant. These details are uploaded onto the secure web based Recruitment Tracker. The Cohort ID generated during the invitation stage will be used the participant identifier. For participants who state they do not wish to be contacted, their details will be not be uploaded and they will not receive any further communication. These details are not visible to the study team.

If required, a reminder letter will be sent to participants.

Participants who independently contact the study team having seen study information i.e. poster / advertising, the local team will upload the contact details onto the PMS, thereafter HIC will be send the invitation pack.

The Recruitment Tracker will document each positive response and with consent participant contact details allowing the study team to efficiently communicate with participants, GPs and secondary care physicians.

For data management purposes, identifiable information, completed consent forms and anonymised study data will be securely stored in locked cupboards, password protected databases and spreadsheets in the University of Dundee. Identifiable information will be stored separately from study data. Authorised members of the trial and data management team will have access to identifiable information to allow the management of study visits.

#### 5.1.4.1 Managing Responses

For all recruitment methods only the Personal Identifiable Data (PID) of potential participants' giving a positive response will be provided to the research team.

NOTE: PID will be stored on the web-based electronic Patient Management System (PMS) hosted by Health Informatics Centre (HIC) (23). Secure access, via individual password protected accounts, will be provided to delegated research team members.

- RN or delegate will contact positive respondents via phone, email or letter (as per patient preference) to perform telephone pre-screening i.e. check inclusion and exclusion criteria. Those participants not noting any exclusion criteria will receive the full PIS (the RN will send by mail or email), be invited to attend a baseline visit and be given enough time to consider their participation. All questions will be answered fully before informed consent is obtained.
- Where no response is received to phone call / email after 3 attempts a reminder letter with a further PIS, reply slip and pre-paid reply envelope will be sent to the patient (to check their willingness to participate).

#### 5.2 CONSENTING PARTICIPANTS

At the combined screening and baseline visit, written informed consent will be obtained by the local PI or delegate. The Delegation Log will detail staff (e.g. research nurses) who are appropriately qualified and trained staff and delegated to obtain informed consent. Where a participant requests to speak with a physician from the study team the consent process will not be completed until the participant has spoken to the physician and had all their questions answered to their satisfaction. Normal capacity is presumed (initial judgement is made by clinical team performing pre-screening; in addition, the RN will liaise with PI if any doubt or concern is raised when the PIS is provided / screening visit booked), where there is concern the PI or medically qualified delegate will assess capacity prior to any informed consent discussion; severe cognitive impairment (in the opinion of the investigator) is an exclusion criterion. Informed consent will cover all study procedures. A copy of the signed Informed Consent form will be retained at the study site and filed in the securely stored Investigator Site File (ISF) with an additional copy filed in the participant's medical notes.

Co-primary outcome data, including recruitment source will be provided via the PMS; this will be updated and Enrolment Log (filed within ISF) will be completed for all consented participants. Additional monthly Enrolment Log updates will be sent to the Trial Manager / delegate.

Eligibility and Informed Consent will be monitored as per the study Monitoring Plan

For participants recruited within NHS Fife specific written consent will be sought to link to routinely collected prescription, primary and secondary care use and social care data (see Section 0 and 0). This will be used to cross-validate information given by participants as preparatory work for using

such routinely collected data in a future large trial. The medication prescription data record linkage will be used as one of the measures to assess medication adherence.

A verbal consent check will be performed at each subsequent visit; recorded in participant medical record.

#### 5.3 SCREEENING FOR ELIGIBILITY

Pre-screening and screening will be carried out by the RN or delegate; all inclusion and exclusion criteria will be checked as fully as possible.

All pre-screening and screening activity will be captured on the Screening Log (filed within ISF) and/or Excel Screening Activity spreadsheet: this co-primary outcome data will include number of patient notes reviewed; potential participants pre-screened and screened; reasons for ineligibility. Monthly Screening Log Excel spreadsheet updates will be sent to the Trial Manager / delegate. No PID will be provided to the study team.

The combined screening and baseline visit will take place at a local clinic or research facility, depending on where is most convenient for participants in each area.

The final eligibility check will be performed at the combined screening/baseline visit and prior to randomisation all inclusion and exclusion criteria will be confirmed by the PI/medically qualified delegate. This signed eligibility confirmation will be recorded in the Case Report Form (CRF) and medical notes.

#### 5.4 INELIGIBLE AND NON-RECRUITED PARTICIPANTS

Screening data will be retained for participants that are not subsequently randomised; this will not contain PID. The reason(s) for ineligibility will be:

- Logged on the study Screening Log
- Explained to the participant and any questions they have will be answered.
- Ineligible participants will be thanked for their interest; any relevant clinical information will be added to their hospital notes and communicated to their GP (with consent) and reassured that by withdrawing from the study this will not affect their future medical care. Rescreening, previously ineligible participants, will not occur in this pilot study.

#### 5.5 RANDOMISATION

#### 5.5.1 Randomisation

After successful screening for eligibility and safety, and completion of baseline outcome measures, participants will be randomised on a 1:1:1 allocation ratio via a web-based system TRuST, run by the Tayside Clinical Trials Unit (TCTU) and hosted by HIC, to preserve allocation concealment. The TRuST system will be based on the study protocol; system validation and User Acceptance Testing will follow HIC and TASC SOPs; CI review and approval will be carried out prior to the live system release.

The study arms are:

- Continue oral iron
- Stop oral iron
- Stop oral iron and give IV iron (as per local formulary).

Direct care physicians (i.e. GP or hospital clinician) will receive written notification of the randomisation allocation. Participants will be verbally informed of treatment allocation (telephone visit). Treatment allocation will be recorded in the participant medical record.

Where web-access is not possible at site, emergency randomisation will be provided by TCTU via [contact]; following the TCTU Unblinding Work Instruction. Verbal notification of randomisation will be provided; email record of emergency randomisation will be provided when web-access is available) and filed in the participant medical record.

A minimisation algorithm with a random element will be used to ensure balance across recruitment centres and key baseline measures. Randomisation will be stratified by site, and further balanced using minimisation. Haemoglobin after minimum 8 weeks of oral iron (>=100g/L vs <100g/L), ferritin prior to commencement of oral iron (>=50ug/L vs <50ug/L) and six minute walk distance (>=300m vs <300m) will be the minimisation variables.

Only those involved with development and maintenance of the system will have access to the treatment allocations during the study; those involved with outcome assessment or statistical analysis will not have access to allocation until the point of the final analysis after database lock. Unblinding will occur following OC database lock; the CI will formally request unblinding.

#### 5.5.2 Withdrawal procedures

Participants will be withdrawn from the study if a) they request to withdraw, or b) they lose capacity to give informed consent (as assessed by the clinical judgement of the local PI/delegate). Withdrawal will be as per Sponsor SOP and documented using the Sponsor Withdrawal Form.

Any physician, involved in direct care (i.e. GP or hospital clinician) or study care (i.e. PI/ medically qualified delegate), using their clinical judgement may withdraw a study participant from their randomised treatment. This may occur due to the occurrence of:

- an adverse event (AE)
- the onset of a symptom that is deemed related to the study participation or related procedures
- the onset of a symptom that is an exclusion criteria
- any other reason which in their clinical judgement requires the participant to be withdrawn

Patients withdrawn from randomised treatment will remain in the study (with consent) for safety follow-up and outcome measures, and will be included in the intention to treat analysis (ITT) but will be censored in per-protocol analyses. If withdrawal is due to a study intervention product related AE it will be logged as such on the Adverse Event Log. All reasons for withdrawal will be noted in the participant's CRF and medical notes.

If at any time the participant formally withdraws his/her consent for future participation and disclosure of future information, no further evaluations will be performed and no additional data will be collected. With consent, data collected before withdrawal will be retained and used in the study analysis; where withdrawal includes data, and if this occur before data base lock, the data will be excluded from analysis. Although a participant is not obliged to give reason(s) for withdrawing consent prematurely, if the participant appears lost to follow up, the CI will make a reasonable effort to ascertain the reason(s), while fully respecting the individual's rights, and will demonstrate that everything possible was done in an attempt to find any participant lost to follow-up. Those lost to follow-up or withdrawn will be identified and a descriptive analysis of them provided, including the reasons for their loss and its relationship to treatment and outcome.

A dropout rate of 30% is assumed, we therefore aim to recruit and randomise up to 84 participants to ensure that we have 20 completed participants per treatment arm (60 in total).

### 6 INVESTIGATIONAL PRODUCT

Note: This study is a non-CTIMP.

#### 6.1 ACTIVE INVESTIGATIONAL PRODUCT

The study compares three strategies of care: withdrawal of oral iron, continuation of oral iron, or switching from oral iron to intravenous Iron. All these drugs are normally used in the NHS to treat iron deficiency anaemia. The study does not compare the safety or efficacy of these iron preparations.

- Oral iron has been previously prescribed by the direct care physician (i.e. GP or hospital clinician).
  - At randomisation continuation or discontinuation will be notified in writing to the direct care physician and verbally (via telephone visit).
- IV Iron will be prescribed by the site PI or delegated medically qualified research team member.
  - Local policies will apply.
  - Ferric carboxymaltose or iron sucrose will be permitted, this reflects current clinical practice where different sites use different preparations.
  - The dose and administration time of IV iron will be calculated using both the participant's bodyweight and the haemoglobin level. This is in line with current prescribing practice.
  - NHS emergency/resuscitation facilities are available at each study site.
  - In a suitable clinical setting the participant will receive IV iron infusion according to local policies for the safe administration of IV iron.

#### 6.2 STUDY INVESTIGATIONAL PRODUCT STORAGE

Oral and IV iron preparations will be purchased and stored within Pharmacy as per product storage information and as per local Pharmacy guidelines. The quality assurance of storage conditions will be as per local Pharmacy procedures.

#### 6.3 STUDY INVESTIGATIONAL PRODUCT REFERENCE SAFETY INFORMATION

Summary of Product Characteristics (SmPC) will be as per locally used oral and IV iron preparations.

The potential side effects of IV iron will be communicated to participants in writing via the PIS and verbally during informed consent discussion.

The current copies of the SmPC for the oral and IV iron preparations in use at site, will be filed in the ISF for the purpose of detecting any potential Adverse Drug Reaction (ADR) related to IV iron therapy.

The PI is responsible for ensuring that:

The research team has easy access to the SmPC.
 NOTE: The PI / medically qualified and delegated individual will be responsible for assessing

severity and causality for any and all potential Adverse Drug Reactions.

• Oral and/or IV iron preparation changes are communicated to the CI/ delegated Trial Manager.

#### 6.4 ACCOUNTABILITY PROCEDURES

No study drug accountability will be required.

- IV iron accountability will supervised by the NHS Pharmacist at each study site and as per local NHS Pharmacy prescribing, dispensing and drug administration policy.
- Oral iron accountability will be supervised by a Pharmacist and as per local prescribing, dispensing and drug administration policy.

#### 7 STUDY ASSESSMENTS

#### 7.1 OUTCOME ASSESSMENTS

At each site study assessments (baseline and follow-up outcome assessments) will be carried out by a Research Nurse (RN), or other appropriately trained and delegated individual. The follow-up assessment will be carried out by a blinded RN. This is required to maintain treatment allocation blinding: i.e. the outcome assessments must be collected by a different blinded RN, and not the individual undertaking randomisation. Where this is not possible a deviation will be recorded on the study Deviation Log.

- Assessments are scheduled as per the Study Matrix (Table 4); additional instruction is provided via the Operations Manual.
- All study data will be reported using the study CRF; entered into OC.

- The PMS will be used to track and manage participant study visits; access will be restricted to delegated members of the research team.
- Visits will be recorded in the patient medical record, including all trial data relevant to a participant's general medical history.

#### 7.1.1 Screening and Baseline Visit

See Study Matrix (Table 4).

At screening/baseline the following will be collected from participants and their medical notes:

- Inclusion / exclusion criteria check
- Demographic information including home circumstances and use of mobility aids
- Medical history and medication review
- Height and weight

Additionally the following will be performed:

- 10ml of non-fasted blood will be taken for local laboratory haematological and biochemical analysis:
  - Haemoglobin, ferritin, c-reactive protein, creatinine and estimated GFR (using CKI-EPI equation)

Local laboratory ranges will apply.

## Samples taken at this visit are baseline samples and the results are NOT required to determine eligibility:

- Eligibility assessment requires haemoglobin and ferritin results from before oral iron treatment started and haemoglobin level after a minimum of 8 weeks of oral iron therapy.
- > C-reactive protein baseline samples will NOT be used to determine eligibility.
- Screening creatinine and eGFR sample results will be within 12 months of study entry; if this is not available baseline creatinine and eGFR results will be used to determine eligibility.
- Assessment of Physical function is carried out using the following widely used standardised clinical tests of walking speed, static and dynamic balance abilities:
  - Short Physical Performance Battery (SPPB) (15). This group of measures combines the results of the gait speed, chair stand and balance tests.
  - Six-minute Walk Test. This provides walking speed.

Details of the procedures and equipment used for these tests of physical function will be provided in the study Operations Manual.

- Health and social activity will be collected using the following self-reported questionnaire data collection tools (non-validated tools are provided as appendices):
  - Oral Iron Use Scale self-reported, Likert scale (Appendix 2).
  - Fatigue Severity Score (19) self-reported, validated tool
  - Patient Reported Anaemia Symptoms self-reported scoring at the baseline and the end of each month (Appendix 1).
  - EQ5D-5L (quality of life) (16) self-reported, validated tool.
  - 15D (health related quality of life) (20)– self-reported, validated tool.
  - NEADL score (activities of daily living) (18) self-reported, validated tool to assess and score physical function.
  - Health & Care Use self-reported health care utilisation semi-qualitative questionnaire (Appendix 3).

#### 7.1.2 Telephone Visit

Following randomisation, which is completed by the unblinded research team member, the telephone visit will be performed by the delegated unblinded research team member to inform the participant of treatment allocations.

For participants randomised to receive the iron infusion, the delegated unblinded research team member will contact the relevant NHS team to schedule the visit.

The unblinded research team member will send the Recruited GP Letter to advise GP of treatment allocation.

NOTE: Randomisation will be completed by a different (unblinded) member of the research team, and not the research nurse who will carry out the follow-up visit; this will assure blinded assessment.

#### 7.1.3 Iron Infusion Visit

IV iron administration is a routine procedure in the NHS. Local policies and procedures will apply.

The infusion will be administered by a Registered Nurse / appropriately qualified member of the NHS team. The research team will remain blinded to treatment allocation.

The unblinded RN or delegate will attend the infusion visit.

#### 7.1.4 Follow-up Outcome Assessment Visit

See study matrix (Table 4)

The following will be performed by the blinded RN at the outcome assessment visit:

- 5ml of non-fasted blood will be taken for local laboratory haematological and biochemical analysis:
  - Haemoglobin and Ferritin
- Assessment of Physical function:
  - Timed up and Go Test (TUG).
  - Short Physical Performance Battery (SPPB)(15).
  - o Six-minute Walk Test.

Details of the procedures and equipment used for these tests of physical function will be provided in the study Operations Manual.

- Health and social activity will be collected using the following self-reported questionnaire data collection tools (non-validated tools are provided as appendices):
  - Fatigue Severity Score (19)
  - o Patient Reported Anaemia Symptoms
  - EQ5D5L (quality of life) (16, 17)
  - o 15D (health related quality of life) (20)
  - NEADL score (activities of daily living) (18)
  - o Health & Care Use
  - Participant experience and views (Appendix 4)

For participants randomised to receive oral iron the unblinded RN will telephone the participant to complete the Oral Iron Use Likert Scale.

After study assessments have been carried out, and to preserve blinding, the following will be collected from participants and their medical notes:

- Adverse events
- Medication review.

Participants will be provided with iron specific dietary advice (24) at the end of the Follow-up visit.

At the end of study participation the GP will resume care and iron prescribing; additionally:

- the RN will direct the participant to contact their GP
- the GP will be directed (via GP letter recruited) to review Visit 4 Hb and ferritin results.

#### 7.2 SAFETY ASSESSMENTS

Adverse events will be collected at visit 2 and 4 by direct questioning of participants regarding health and social care contacts, hospitalisations and new symptoms. Details of current medication will be collected at visit 4. The participant's hospital medical record will be reviewed at visit 4; details of all AEs and concomitant medicines will be collected and recorded.

NOTE: Where a discrepancy is identified between participant and medical record reported AE / concomitant medication the PI, or medically trained delegate, will clarify and define the data to report; this decision will be recorded in the medical record.

AEs and concomitant medications are not collected at Visit 3 for the IV iron treatment group; the scientific justification for not collecting this data at Visit 3 is to prevent skewed/over- reporting due to additional data collection.

Where possible to investigators should remain blinded to treatment allocation.

The PI / medically qualified and delegated individual will be responsible for assessing severity and causality for any and all AEs and potential ADRs. Section 4.8 of the relevant SmPC will be used as reference safety information for the assessment of ARDs.

NOTE: SmPC will be as per locally used oral and IV iron preparations.

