#### Table 4: Study Matrix

	Visit 1	Visit 2	Visit 3	Visit 4
	Combined	Randomisation	IV iron	3 month visit
	screening and	and telephone	administration visit	(1/2) weaks)
	baseline visit	call (+1 to 4 days)	(within 2 weeks of	(+/- 3 weeks)
			randomisation)	
Informed consent	X	X	X	Х
Inclusion/Exclusion Criteria	Х			
Demographics and medical	Х			
history				
Adverse Events Recorded		Х		Х
Height and weight	Х			
Medications	Х			Х
Oral Iron Use Scale	Х			X¶
Haemoglobin	Х			Х
Ferritin	Х			Х
C-reactive protein	Х			
Creatinine	X*			
eGFR	X*			
Short physical performance	Х			Х
battery				
Six-minute walk distance	Х			Х
Fatigue Severity Scale	Х			Х
Patient reported anaemia symptoms &	х			х
Quality of Life EQ-5D-5L & 15D	Х			Х
questionnaires				
Activities of Daily Living	Х			Х
(Nottingham EADL score)				
Health & Care Use	Х			Х
questionnaire				
Participants' experiences semi-				Х
qualitative questionnaire				
Randomisation (telephone call)		Х		
IV iron administration (if			Х	
required)				
Nutritional advice leaflet				Х

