#### 9 STATISTICS AND DATA ANALYSIS

#### 9.1 SAMPLE SIZE CALCULATION

Since this is a pilot study, under CSO guidance, no formal sample size calculation is provided – indeed this pilot study will furnish indicative data to allow a sample size calculation for the full trial. We will aim to have 20 completed participants in each arm (60 in total). The target is set at 20 completed participants per arm so as to have sufficient variability in response to provide estimates for future sample size calculation. We also would like to have a sufficient number to examine the feasibility of the recruitment pathways we are proposing. It is also in line with current practice in which a pilot study sample size is ~40-50 for a two-arm trial. Assuming a dropout rate of 30%, we therefore plan to recruit and randomise a total of 84 participants. We will recruit for a maximum of 15 months at four sites (total target N=84).

Linked NHS Fife prescribing and health and social care use data will used for statistical modelling; this will use data from a maximum of 21 participants. Our aim is to test the process of obtaining linked data and to conduct preliminary data verification to inform the main study; to obtain standard deviation and mean outcome variables and to calculate the sample size for the main study and not to obtain statistical results of significance.

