#### 10.1 RECORDING AND REPORTING AEs AND SAEs

AEs and SAEs will be recorded from the time of written informed consent until the last study visit.

- Only AEs which have resulted in the participant seeking advice or treatment from a healthcare professional will be recorded.
- The PI or delegate will ask about the occurrence of AEs and hospitalisations visits 2 and 4 only.
- Once the Investigator becomes aware that an AE or SAE has occurred in a study participant, they
  must enter the information into the CRF AE Log and entered (in a timely fashion) into the
  OpenClinica database.

• Participants with unresolved AEs at the last study visit will be followed up until resolution or 30 days after their last study visit, whichever is sooner.

An SAE occurring to a research participant will only be reported as per HRA guidelines to the main REC, and copied to the Sponsor (as per University of Aberdeen SOP) via [contact], where in the opinion of the Chief Investigator the event was:

Related - that is, it resulted from administration of any of the research procedures, and

*Unexpected* – that is, the type of event is not listed in the protocol or Reference Safety Information (section 6.3) as an expected occurrence.

unless meeting a AE/SAE reporting exception category, as outlined in section 10.1.1 (below).

	Who	When	How	To whom
SAE	Chief Investigator (CI)	Within 15 days of the	SAE report form for non-	Main REC for the
		CI becoming aware of	CTIMPs	study.
		the event		
Urgent safety	Chief Investigator (CI)	(i) Immediately	(i) By telephone	Main REC: study
measures	or sponsor	(ii) Within 3 days	(ii) Notice in writing setting	co-ordinator will
	Or exceptionally by		out the reasons for urgent	acknowledge
	local principal		safety measures and the	within 30 days
	investigator (PI)		plan for further action	

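### After treatment starts, the only scheduled event enquiry and record review are at Visit 4, and no step is stated for participants who have no Visit 4

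*Protocol*

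**What the plan says.** Section 7.2 places direct questioning about events at Visits 2 and 4 and current medication at Visit 4. It adds that the participant's "hospital medical record will be reviewed at visit 4; details of all AEs and concomitant medicines will be collected and recorded". Section 10.1 confirms the limit: "The PI or delegate will ask about the occurrence of AEs and hospitalisations visits 2 and 4 only". In Table 4 the row "Adverse Events Recorded" is marked at Visits 2 and 4 alone, and there is no row for vital status. Section 7.1.4 puts the adverse event collection, the medication review and the care use questionnaire at the follow-up visit.

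The outcomes that need these data are in Table 3 and section 2.2.2: all-cause mortality, health care use (including transfusion and hospitalisation) and crossover at 3 months. Section 9.2 says that analyses will be by intention to treat and include everyone randomised.

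On early leavers, section 5.5.2 keeps participants who only stop their randomised treatment in follow-up. It withdraws from the study those who ask to leave or where "they lose capacity to give informed consent", and it stops all data collection when consent to future data is withdrawn. For those lost to follow-up it asks for tracing and for reasons. It also promises a description of those lost or withdrawn that relates their loss to treatment and outcome. On numbers: "A dropout rate of 30% is assumed" (section 5.5.2), and "we therefore plan to recruit and randomise a total of 84 participants" (section 9.1).

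**The concern.** A record review does not need the participant in the room, but the protocol schedules it only as part of a visit. Someone who dies before 3 months cannot attend that visit, and someone who is acutely ill or unhappy with the allocation is less likely to. Section 10.1.1 itself expects very high levels of illness in this population. Active ascertainment of death, admission, transfusion and crossover would then be most complete in those well enough to attend.

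At stake are the pilot's early figures for these outcomes, and its answer to whether they can be collected in a main trial. The loss could also differ between arms, because willingness to stay may depend on the allocation. A statistical analysis plan cannot repair this later, since the data would not have been collected.

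**Working it through.** **The plan's own figure.** Inputs: 60 completers (20 per arm), 30% dropout and 84 randomised, from sections 5.5.2 and 9.1.
- Required number = 60 / (1 − 0.30) = 85.7, so 86. The stated 84 is within two of this.
- Going back: 84 × 0.70 = 58.8 completers (19.6 per arm). Exactly 60 completers of 84 means (84 − 60) / 84 = 28.6% dropout.

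**Participants without Visit 4.** Dropout is read here as having no Visit 4.
- 0.30 × 84 = 25.2, about 25; per arm 25.2 / 3 = 8.4 if dropout is equal across arms.
- If exactly 60 complete: 84 − 60 = 24.
- This is a ceiling. It includes people who withdraw consent to future data, for whom section 5.5.2 rightly forbids collection. The protocol does not give the split.

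**Share reachable by linkage.** Section 9.1 gives a maximum of 21 linked participants, from Fife: 21 / 84 = 25%. With equal dropout across sites, 0.30 × 21 = 6.3 are in Fife and 0.30 × 63 = 18.9 are elsewhere.

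**Deaths.** The protocol gives no death rate. As an assumption, 1% to 5% at 3 months gives 84 × 0.01 = 0.84 to 84 × 0.05 = 4.2 deaths. Nobody who dies before Visit 4 can be questioned there.

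**What remains for a participant without Visit 4:**
- *Visit 2.* The call comes one to four days after the baseline visit, with randomisation, and the infusion is scheduled within two weeks of randomisation. It is not a post-treatment enquiry.
- *Visit 3.* Section 7.2 deliberately collects no events here. An unblinded team member attends the infusion (section 7.1.3), and iron treatment data go into a separate file kept by the unblinded nurse (section 8.1). Receipt of intravenous iron is therefore known without Visit 4.
- *Logging on awareness (section 10.1).* Any event must be entered once the investigator knows of it. This is passive. Recording also ends at the last study visit, which for someone with no Visit 4 could be read as Visit 2 or 3.
- *Tracing (section 5.5.2).* It seeks the person and the reason for loss. No record check is named.
- *Records as source data (section 8.1).* Notes and electronic records are named as the source for admissions and prescriptions, but without a time point or a task.
- *Fife linkage (section 8.1).* It runs after database lock, for cross-validation, in a file kept outside the study database. It covers prescriptions and hospital and GP contacts, and no death register is listed.

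None of these is an active, scheduled check at 3 months that covers all four sites.

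**The case against.** The strongest reply is that the protocol does plan for these events. Death and hospitalisation meet its definition of a serious adverse event, and such events must be logged on awareness whatever the visit. Tracing a person who misses Visit 4 would usually bring a death to light. People who stop only their treatment stay in follow-up. The wording in section 7.2 can be taken as a time (3 months) and not as a condition of attendance. The Operations Manual, the case report form and the sponsor's withdrawal procedure are not shown and may already say so. Mortality and health care use are also listed as feasibility outcomes, so their incompleteness would itself be a result of the pilot.

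Much of this stands. A reader might infer that early leavers have no planned ascertainment of death, admission or iron at all, or that deaths would be learned of only by chance. The documents do not support that: awareness logging and tracing are planned routes, and intravenous iron at Visit 3 is witnessed and filed separately. A reader might also infer that the loss-of-capacity rule in section 5.5.2 must be rewritten. That depends on consent and legal wording that is not shown, and the rule is not contradicted elsewhere in the protocol.

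The reply does not supply a scheduled step. Awareness is passive, tracing is aimed at reasons, and section 8.1 names a source without assigning the work. Section 5.5.2 nevertheless promises to relate loss to outcome, which requires outcomes in those lost. If incompleteness is to be a feasibility result, it should reflect what the records can yield and not whether anyone was asked to look.

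**Conclusion.** The point holds in this form: no active, scheduled ascertainment of vital status, hospitalisation, transfusion, oral iron use or later crossover is specified for participants without a Visit 4. It concerns at most about 25 of 84 at the protocol's own dropout, about 19 of them outside Fife, and fewer after consent withdrawals. It includes anyone who dies first. These counts assume that dropout means no Visit 4 and is equal across sites.

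The 3-month mortality, health care use and crossover figures are likely to be incomplete in a way related to illness. The size of any resulting bias cannot be calculated, because the protocol gives no event rates for those who stay or leave. The co-primary recruitment outcomes are untouched. This should be changed because it alters what is collected and the change is cheap, but it does not undermine the pilot.

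**What to change.** In sections 7.2 and 10.1 and in Table 4, state that the record review is carried out at the 3-month date for every randomised participant, whether or not Visit 4 is attended, except those who withdrew consent to future data. It should cover vital status, admissions, transfusions and iron prescribed or infused. Add a matching row to Table 4. In section 10.1, let adverse event and serious adverse event recording run to that date and not to the last visit attended. For those who do attend, the review can stay after the outcome assessments, as now, to protect blinding.

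The cost is a small change to the protocol and consent form, and at most about 25 further record reviews by existing site staff.
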